#### ***4.7.2 Maternal Secondary Outcomes***

a) gestational diabetes

- b) preeclampsia
- c) cesarean delivery
- d) shoulder dystocia
- e) weight, adiposity, BP, fasting glucose, lipids, C-reactive protein, vitamin D, leptin, adiponectin
- f) Homeostatic Model Assessment (HOMA) score, a measure of insulin resistance (with the assistance of a computer program available online from the University of Oxford Diabetes Trial Unit)
- g) diet quality (diet and metabolomics assessment)
- h) physical activity
- i) sleep quality and duration
- j) measures of stress and self-efficacy

#### ***4.7.3 Fetal and Neonatal Secondary Outcomes***

- a) birth weight
- b) newborn length
- c) % body fat measured by ADP
- d) cord blood/ C-peptide
- e) hypoglycemia
- f) NICU admission, length of stay
- g) birth trauma

#### ***4.7.4 Infant Secondary Outcomes***

- a) weight
- b) length
- c) sum of skinfolds
- d) duration of breastfeeding
- e) infant age at which solid foods were introduced
- f) diet quality
- g) physical activity

#### ***4.7.5 Methods to Minimize Ascertainment Bias***

Pre-pregnancy weight will be determined prior to randomization, and data collection visits will be conducted by trained staff, blinded to group allocation.

Participants randomized to the Usual Care group will receive educational advice to follow the guidelines established by the USDA MyPlate.gov diet recommendations for pregnancy and lactation, as well as the US Dietary Guidelines, 2010. Usual Care participants will be invited to attend group sessions offered quarterly at the hospital during the study period that provide general well care for new moms and their babies but do not include detailed information or behavioral intervention regarding diet, physical activity or GWG. The Usual Care Group will also receive weekly electronic newsletters developed by Prentice Hospital that provide general information about pregnancy, infant care and transitioning into motherhood.

The Usual Care group will attend the baseline and all data collection visits (**Table 3**) conducted by trained research staff blinded to the group assignments. This approach will maintain separation of the study and the clinical follow-up.

## 5 Statistical Considerations

### 5.1 Data Relevant to the Primary Outcome

Studies have shown typical standard deviations (SD) of 15 lbs (6.8 kg) when assessing gestational weight gain. Additionally, studies have demonstrated that approximately 35% of overweight and obese women will gain more than current IOM recommended weight. Studies examining postpartum weight loss have typical SDs of 12 lbs (5.5 kg).

### 5.2 Sample Size and Power

The proposed total sample size for MOMFIT is 300 women, with 150 randomized to Active Intervention and 150 to the Control Group. Because this study compares two randomized groups, power is based on an independent 2-sample t-test using a two-sided type I error rate ( $\alpha$ ) of 0.05. Assuming a SD of 15lbs (6.8kg) of GWG, a sample size of 143 women per group is sufficient to attrition to provide 80% power to detect a difference of 5 lbs (2.4 kg) between groups. A difference of 5 lbs was chosen to be clinically significant. It is expected that there will be no more than 5% attrition from randomization through 36 weeks and delivery; thus a total sample size of three hundred patients was chosen.

The anticipation is for no more than 10% attrition for secondary outcomes measured at delivery, and no more than a 20% attrition rate from randomization to 12 month postpartum. **Table 5** shows the specific aims, attrition, and effect sizes detectable for secondary outcomes with 80% power for a sample size of 300 women based on two-sided t-tests and Chi-square tests of association ( $\alpha=0.05$ ).

**Table 5. Effect Sizes Detectable with 80% Power**

Aim	attrition	control mean(SD) or percentage	intervention mean (SD) or percentage
Achievement of IOM guidelines	5%	35%	51.2%
Metabolic profiles (delivery)	10%	Effect size = 0.35	
Metabolic profiles (12 m. postpartum)	20%	Effect size = 0.37	
Infant metabolic profiles	10%	Effect size = 0.35	
Infant weight for length ( $\geq 95\%$ )	10%	15%	4.9%
Complication rates (delivery)*	10%	11%	2.8%
Postpartum weight loss from 36 week visit weight	20%	13 lbs (12lbs)	17.4lbs (12 lbs)

\* composite composed of preeclampsia, shoulder dystocia, or birth injury

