Left uninterrupted, this cycle of perpetual excessive GWG with increasing adverse maternal-offspring consequences could have a devastating public health impact. This prompted the IOM to reexamine and revise the GWG Guidelines in 2009 with limits of 15-25 pounds (7-11.5 kg) in overweight (BMI 25.0-29.9 kg/m^2) and 11-20 pounds (5-9 kg) in obese (BMI  $\geq 30.0$  kg/m^2) women [3]. Lifestyle modifications which have been proven effective among non-pregnant populations [17, 18] have been applied to prevention of excessive GWG in overweight or normal weight women, and the results have been promising in some [19-21] but not all studies [22, 23]. Research is urgently needed to identify and apply effective approaches to lifestyle modification including electronic, technologically enhanced approaches that can be successfully adapted to OW/OB pregnant women of diverse ethnic, racial and economic backgrounds.

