## 3 Study Design

### 3.1 Primary Research Question

Can prenatal diet and lifestyle intervention among overweight/obese pregnant women reduce gestational weight gain? For the purpose of this primary outcome, gestational weight gain is defined as the difference between the maternal weight measured at the 36 week visit and the weight recorded at the Baseline visit.

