### 3.3 Design Summary

A RCT is planned among 300 ethnically diverse OW/OB pregnant women ages 18-45 years to be randomly assigned to the Intervention Group (MOMFIT Lifestyle Change group) or the Usual Care Group (Web-Watcher enhanced Usual Care) group. The MOMFIT behavioral intervention recommends eating the DASH-modified diet and moderate physical activity, primarily walking, adapted through a program of individual visits to tailor calorie/nutrient/activity goals, group coaching sessions, and individualized follow-up contacts. Electronic self-monitoring behavior will be adapted for pregnant/postpartum women via smartphone or Internet access, along with tailored feedback and encouragement from the Lifestyle Coach. Prevention of excessive GWG and achievement of the IOM weight gain goals will be compared between groups, and also whether ongoing adherence to the lifestyle interventions can be sustained through postpartum intervention. Approximately one third of the participants are expected to be minorities and/or from low income backgrounds. In our experience, over

90% of these women have regular computer and/or smartphone access. The primary outcome is gestational weight gain from baseline to near delivery (36 weeks). The secondary outcome is postpartum weight retention between 6 weeks and 12 months postpartum.

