- 3) PA = 1.27 if PAL is 60 min/day or more

During the Individual Visits, each participant will have her own energy needs calculated and her daily dietary calorie goals will be reviewed as indicated in **Table 2**. For weight control purposes in these overweight/obese women, MOMFIT will minimize increases in energy intake. This intentional energy deficit is calculated to enhance energy balance without compromising nutrient density. In order to reduce weight gain but achieve nutrient adequacy, we will recommend 75% and 50% of the calorie goals for overweight and obese participants, respectively as presented in Table 2. Careful monitoring for safety and prevention of weight loss during pregnancy will occur via weekly contacts. Weight gain or loss of 1 pound or more within one week will be further reviewed with the mother.

**Table 2. Calorie needs during pregnancy and lactation for nonobese women compared with recommendations to accompany reduced weight gain goal for overweight/obese MOMFIT participants**

Trimester or phase	Pregnancy and Lactation	IOM Addition Normal Weight	MOMFIT Addition Overweight	MOMFIT Addition Obese
IOM Weight Gain Goals (lbs) *		25-35	15-25	11-20
1 st trimester	Prenatal (kcal)	0	0	0
2 nd trimester	Prenatal (kcal)	340	255	170
3 rd trimester	Prenatal (kcal)	452	339	226
1 st 6 mos.	Breast milk only, no formula (kcal)	330	248	165
1 st 6 mos.	At least half breast milk, plus some formula (kcal)	70	53	35
1 st 6 mos.	Some breast milk, mostly formula (kcal)	0	0	0
2 nd 6 mos.	Breast milk only, no formula (kcal)	400	300	200
2 nd 6 mos.	At least half breast milk, plus some formula (kcal)	200	150	100
2 nd 6 mos.	Some breast milk, mostly formula (kcal)	0	0	0

\*

reference [3]

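### Does the 35% control rate for achieving the IOM guidelines in Table 5 contradict the 35% in Section 5.1?

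*Combined protocol and SAP*

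**What the plan says.** Section 5.1 (Data Relevant to the Primary Outcome) states, citing unnamed studies, that "approximately 35% of overweight and obese women will gain more than current IOM recommended weight". Section 5.2 introduces Table 5 as giving the "effect sizes detectable for secondary outcomes with 80% power for a sample size of 300 women", by two-sided t-tests and chi-square tests at 0.05. The first row of Table 5 is "Achievement of IOM guidelines": 5% attrition, control 35%, intervention 51.2%.

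The IOM goals appear twice as ranges. Section 2.1 says that the IOM acted to "revise the GWG Guidelines in 2009 with limits of 15-25 pounds" for overweight women and 11-20 pounds for obese women. Table 2 in Section 4.4.1 repeats both under "IOM Weight Gain Goals (lbs").

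The Design Summary (Section 3.3) says: "Prevention of excessive GWG and achievement of the IOM weight gain goals will be compared between groups". Section 4.7.2 does not list IOM achievement. Its nearest item is "weight, adiposity, BP, fasting glucose, lipids, C-reactive protein, vitamin D, leptin, adiponectin". The trial's own gestational weight gain (Section 3.1) is the "difference between the maternal weight measured at the 36 week visit and the weight recorded at the Baseline visit". No section says which interval the IOM limits are applied to.

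**The concern.** The same number appears in two adjacent subsections with opposite meaning: in Section 5.1, 35% is the share who do badly; in Table 5 it is the share who do well. That is the usual trace of a rate copied without being turned round. If achievement means not exceeding the upper limit, Section 5.1 implies a control rate of 100 - 35 = 65%, and the Table 5 row starts from the wrong place.

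Reading achievement as within range does not remove the doubt. The plan assumes an SD of 15 lb, and the IOM windows are only 10 lb and 9 lb wide. Under a normal distribution with that SD, a within-range share of 35% is out of reach.

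At stake are the stated detectable effect for a comparison named in the Design Summary, and the risk that an undefined responder endpoint is settled after the data are seen.

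**Working it through.** **Inputs.** 150 women per arm and 5% attrition (Section 5.2 and Table 5), so n = 150 x 0.95 = 142.5 per arm. Power 80%, two-sided alpha 0.05, so (1.960 + 0.842)^2 = 7.849. Rates 35% and 51.2% (Table 5). SD 15 lb (Section 5.1). IOM windows 15-25 lb (width 10) and 11-20 lb (width 9).

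**1. Table 5's own figure.** Unpooled formula: n = 7.849 x [p1(1-p1) + p2(1-p2)] / (p2-p1)^2. With 0.35 and 0.512 this is 7.849 x (0.2275 + 0.2499) / 0.02624 = 142.8 per arm, against 142.5 available. Solving for the detectable rate from 35% gives 51.2% unpooled and 51.4% pooled. The row reproduces, so the only question is what the 35% stands for.

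**2. What other control rates would give.** Same n, power and alpha, pooled formula. Apart from 35% (Table 5) and 65% (Section 5.1 turned round), the control rates are assumptions, because the documents give none.

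| Control rate | Basis | Detectable rate | Difference (points) |
|---|---|---|---|
| 65% | not exceeding, Section 5.1 as written | 79.8% | 14.8 |
| 55% | within range, 10% below (assumed) | 71.0% | 16.0 |
| 45% | within range, 20% below (assumed) | 61.5% | 16.5 |
| 35% | within range, 30% below; equals Table 5 | 51.4% | 16.4 |
| 25% | within range, assumed | 40.5% | 15.5 |
| 20% | within range, assumed | 34.7% | 14.7 |

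The absolute rates move a good deal and the difference hardly at all. If 65% were the true control rate, the printed 16.2-point difference (65% against 81.2%) would have 87.3% power, so the row would be conservative.

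**3. Can both 35% figures hold?** For a two-sided goal, above + within + below = 100%. Setting above = 35% and within = 35% leaves below = 30%. Nothing in the documents excludes this.

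**4. Does the SD of 15 lb exclude it?** Under normality the largest share inside a window of width w is 2 x Phi(w / (2 x 15)) - 1. That is 26.1% for w = 10 and 23.6% for w = 9, both short of 35%. A 35/35/30 split would need SD = w / (z0.65 - z0.30) = w / (0.385 + 0.524), which is 11.0 lb or 9.9 lb.

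The ceiling depends on the shape of the distribution. For a Laplace distribution with SD 15 lb, the scale is b = 15 / sqrt(2) = 10.61 lb and the largest share in a window is 1 - exp(-w / (2b)):
- w = 10: 1 - exp(-0.471) = 37.6%.
- w = 9: 1 - exp(-0.424) = 34.6%.

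The same SD therefore allows about 35% within range when the distribution is more peaked than the normal. This example is not offered as a model for weight gain. It shows only that the SD by itself does not rule out the Table 5 rate.

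**5. What depends on the row.** The sample size comes from the t-test: 2 x 7.849 x (15/5)^2 = 141.3, that is 142 per arm, or 143 with the t correction as Section 5.2 states. The 35% does not enter.

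**The case for a change.** The best case for a change runs as follows. Section 5.1 holds the only background rate in the plan for gain against the IOM limits, and nothing in the plan yields a 35% achievement rate except that number read the other way. The abstract (Section 1.1) speaks of limiting gain to the IOM goals, which suits a not-exceeding definition, and under that definition 35% and 65% cannot both be right. Under the within-range definition, both figures need a 30% share below range that no section states. The normal model is the usual first approximation, and it speaks against a 35% within-range share. Differences in mean gain between BMI classes would make the within-class SD smaller, but in a 50/50 mix the class means would have to differ by about 20 lb to bring it down to 11 lb. The repair would be cheap.

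Part of this stands. Achievement is undefined, the 35% has no citation, and a slip in one of the two places is possible. A mismatch does not follow. The Design Summary names prevention of excess gain and achievement of the goals as two things, and the printed goals have lower as well as upper limits; both favour the within-range reading, under which the figures are compatible. The SD argument needs normality, the same 15 lb in each BMI class, and that SD over the interval to which the IOM limits apply. Section 5.1 calls 15 lb typical and gives neither class nor interval. The missing citation is not peculiar to this row, since no row of Table 5 carries one.

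The worry about choosing a definition after seeing the data is fair in general. Here the limits are published and printed in the plan, and tabulating the shares below, within and above range by arm shows every definition at once.

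**Conclusion.** The concern does not call for a change. The figures are quoted correctly and the arithmetic behind the doubt is sound, but it shows an undefined term and a possible clerical slip, and does not establish a contradiction. Correcting the row under any reading would alter one line of a table of detectable effects. It would not alter the 300 women, the primary t-test or the way any outcome is analysed. The largest effect supported by the plan's own figures is 65% against 79.8% in place of 35% against 51.2%, a detectable difference of 14.8 points instead of 16.2.

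This rests on 142.5 women per arm and on reading the IOM goals as the two-sided ranges printed in Section 2.1 and Table 2. It would weaken if the sponsor's source showed that achievement was meant as not exceeding the upper limit. One of the two statements would then be misworded, and the consequence would still be a wording correction to a secondary row. Within-range control rates such as 25% are assumptions and do not belong in the table.

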
## ***1.2 Study Objective***

To test, in 300 ethnically diverse OW/OB pregnant women, a behavioral intervention aimed at controlling GWG through recommended diet, activity and lifestyle changes that are to be maintained postpartum.

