### 3.2 Secondary Research Questions

- Will adherence to the DASH diet and lifestyle intervention, in addition to reduced GWG, also produce postpartum weight control and other beneficial outcomes related to the following parameters?
- Will metabolic profiles (blood pressure, anthropometry, fasting glucose, insulin or C-peptide, HbA1c, blood lipids and CRP) of mothers and babies be different between the Intervention and Usual Care groups?
- Will prenatal diet and lifestyle intervention in overweight/obese mothers result in fewer complications of pregnancy (preeclampsia, gestational diabetes mellitus (GDM), cesarean birth)?
- Will infants in the Intervention group breastfeed longer, begin solid foods later and have higher quality diets (more fruits, vegetables, dairy, less sugary beverages) than Usual Care group infants at 12 months?
- Is adiposity (percent body fat) and body weight reduced postpartum in mothers and babies in the intervention group compared to Usual Care?
- Do mothers in the Intervention group have higher quality diet (more fruits, vegetables, grams of fiber and nonfat dairy; less saturated fat/trans fat, sugar sweetened beverages) and more minutes of physical activity than mothers in the Usual Care group throughout the study?
- Will diet quality differences be evident as measured by metabolomics assays specifically related to fruit/vegetable and dietary fiber intake as alkylresorcinols (fiber), prolinebetaine (citrus fruit) and S-methyl-L-cysteine sulphoxide (cruciferous vegetables) in maternal urine and cord blood.
- Are measures of sleep quality and duration, depression and stress, self-efficacy and mindfulness in diet, breastfeeding and physical activity more favorable in the intervention group compared with the Usual Care group?

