(diffusion editing) and the low molecular weight components (Carr-Purcell-Meiboom-Gill pulse sequence) respectively. Ultra-performance liquid chromatography (UPLC)-MS profiling will be used in general screening mode using in-house methods [50]. Targeted analysis will be conducted for alkylresorcinols (fibre), prolinebetaine (citrus fruit) and S-methyl-L-cysteine sulphoxide (cruciferous vegetables) using a combination of UPLC-MS and NMR methods. Data will be analyzed using multivariate statistical tools including linear projection methods and cluster analyses in order to identify candidate metabolic biomarkers associated with obesity or intervention. Candidate metabolic biomarkers of obesity in pregnant mothers at baseline and 36 weeks will be identified using available databases, by further analytical experiments such as 2-dimensional NMR pulse sequences including homo and heteronuclear correlation spectroscopy, LC-NMR-MS etc and by statistical correlation spectroscopy methods [48]. Several mathematical strategies will be applied to achieve higher sensitivity in detecting panels of inter-related biomarker candidates associated with maternal weight gain, maternal BMI and infant birthweight and adiposity. These methods will accommodate the specific challenges posed by spectral data including low sample:variable ratio, colinearity of predictor variables, confounding factors or co-morbidities correlated with both predictor and outcome variables etc. A flexible framework based on generalized linear models will be implemented to identify univariate and multivariate relationships of predictor variables with outcomes while statistically accounting for potential confounding effects observed in human studies. The choice of a model will be considered based on the probability distribution of a clinical outcome and both Bayesian and conventional maximum likelihood inferences will be made.

In addition to the ASA24 nutrient data, diet quality differences will be measured by metabolomic assays specifically related to fruit/vegetable and dietary fiber intake as alkylresorcinols (fiber), prolinebetaine (citrus fruit) and S-methyl-L-cysteine sulphoxide (cruciferous vegetables) in maternal urine and cord blood.

**Weight** will be measured without shoes, wearing light clothing on a calibrated beam balance scale at the Baseline visit, and at 24-28 week, and 35-37 weeks prenatal visits and the 6 week and 12 month postpartum visits.

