### ***4.7 Study Outcome Measures and Ascertainment***

#### ***4.7.1 Primary Outcome***

The primary outcome is GWG as assessed continuously by the difference between the maternal weight measured at the 36 week visit and the baseline visit.

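### Postpartum weight has no single definition, and the version powered in Table 5 (loss from the 36-week weight) has an expected arm difference of zero when a gestational weight-gain benefit is fully kept

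*Combined protocol and SAP*

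**What the plan says.** Four places describe the outcome:

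- Section 3.3: "The secondary outcome is postpartum weight retention between 6 weeks and 12 months postpartum". It does not say against which weight retention is measured.
- Section 3.2 asks whether "body weight reduced postpartum in mothers and babies in the intervention group compared to Usual Care", with no time point or reference weight.
- Section 4.7.2, item (e), begins "weight, adiposity, BP, fasting glucose, lipids". Again there is no time point, contrast or reference weight.
- Table 5 powers "Postpartum weight loss from 36 week visit weight": 13 lb in control against 17.4 lb in intervention, SD 12 lb in each arm, 20% attrition. Section 5.2 gives that attrition for 12 months postpartum, so the row refers to loss by 12 months.

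The primary outcome in 4.7.1 is the "difference between the maternal weight measured at the 36 week visit and the baseline visit", so the 36-week weight serves both outcomes. Section 4.4.3 schedules maternal weight "at the Baseline visit, and at 24-28 week, and 35-37 weeks prenatal visits and the 6 week and 12 month postpartum visits".

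On analysis, 5.4.1 says linear or logistic models will be fitted when groups are compared, without naming covariates, and treats mixed models of gain and retention as further exploration. Section 5.4 offers age, pre-pregnancy BMI and race as examples of adjustment factors, in the paragraph on GWG.

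**The concern.** The intervention is meant to lower the 36-week weight. Loss measured from that weight starts from a point that the intervention has already moved. An arm that gained less has less to lose, so a good result on the primary outcome pulls this measure towards zero or below.

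Section 3.2 asks whether intervention women weigh less postpartum. The Table 5 contrast could be null, or significant against the intervention, while they do weigh less at 12 months. With several descriptions and none designated as the main one, the headline postpartum result could also depend on a choice made after the data are seen.

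**Working it through.** **Inputs.** Two-sided alpha 0.05 and 150 women per arm (5.2). Attrition of 20% to 12 months (5.2), so 150 × 0.80 = 120 per arm. SD of postpartum loss 12 lb and SD of GWG 15 lb (5.1). Planned GWG difference 5 lb (5.2).

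**Table 5 reproduced.** The difference is 17.4 − 13 = 4.4 lb. With SD 12 lb and 120 per arm, the two-sample t-test has 80.8% power (81.1% by the normal approximation). The detectable difference at 80% power is 4.36 lb. The row is arithmetically correct.

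**What the row measures.** For one woman, loss from 36 weeks = (36-week − baseline) − (12-month − baseline). Let G be the GWG benefit (control minus intervention) and R the 12-month benefit relative to baseline. For the same women and the same 36-week value:

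arm difference in loss (intervention − control) = R − G.

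This is algebra and needs no SD. In the trial as run it is approximate, because attrition differs at 36 weeks (5%) and 12 months (20%), and 5.4.3 allows a care-provider weight to stand in at 36 weeks.

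**Size.** With G = 5 lb, SD 12 lb and 120 per arm, the standard error is 12 × √(2/120) = 1.55 lb. By noncentral t:

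| 12-month benefit R | Table 5 difference R − 5 | Chance of a significant result |
|---|---|---|
| 5 lb (fully kept) | 0 lb | 2.5% each way |
| 3 lb | −2 lb | 25% against the intervention |
| 0 lb | −5 lb | 90% against |
| 7 lb | +2 lb | 25% in favour |
| 9.4 lb | +4.4 lb | 81% in favour |

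On top of the planned GWG benefit, the powered advantage therefore needs a 12-month benefit of 5 + 4.4 = 9.4 lb.

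**Precision of the comparison that estimates R.** The documents give no SD for change from baseline to 12 months. From the two SDs in 5.1 and an assumed gain–loss correlation ρ, SD = √(15² + 12² − 2ρ × 15 × 12) = √(369 − 360ρ). The detectable difference at 120 per arm is 0.363 × SD.

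| Assumed ρ | SD (lb) | Detectable (lb) | Power at R = 5 lb |
|---|---|---|---|
| 0.75 | 9.9 | 3.6 | 97% |
| 0.625 | 12.0 | 4.4 | 90% |
| 0.40 | 15.0 | 5.4 | 73% |
| 0 | 19.2 | 7.0 | 52% |

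These figures are before any gain from adjusting for baseline weight.

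**The case against.** There is a substantial case on the other side.

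- *Loss from 36 weeks suits the design.* The postpartum programme in 4.4.1 sets new weight-loss goals, and loss from 36 weeks measures that phase. Zero is then the right answer when both arms lose the same amount. This stands: the row is valid for that question, but it does not answer the one in 3.2.
- *Section 3.3 may already mean the right thing.* Section 2.1 uses postpartum weight retention for pounds kept after gestational gain. On that usage 3.3 would show a kept benefit. This also stands as a possible reading. But no reference weight is stated, and if 3.3 means change from 6 weeks to 12 months, it cancels any benefit already present at 6 weeks.
- *R can be recovered as G plus the loss difference.* This is only approximate, for the attrition and substitution reasons above. A test of R also needs the covariance of the two parts, which amounts to analysing change from baseline directly.
- *Table 5 has a 12-month effect size of 0.37 for metabolic profiles*, and 3.2 counts anthropometry among these. That row names neither weight nor an SD, so it does not settle the definition.

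Three stronger readings are tempting but not supported. First, a reader might infer that the objective requires the weight difference itself to persist. Section 1.2 speaks of "lifestyle changes that are to be maintained postpartum", which refers to behaviours. Second, a reader might infer that the plan will compare raw 12-month weight without adjustment and so with little power. No section specifies such a test; the gap is that covariates are not named. Third, a reader might infer that a 12-month comparison is missing altogether. Weight is a listed secondary outcome and is collected at 12 months.

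**Conclusion.** The point holds as one of definition and choice of contrast, and should be fixed. Postpartum weight is described inconsistently. The only description powered in pounds has an expected arm difference of zero when the planned 5 lb benefit is fully kept, and −2 lb when 3 lb of it is kept. No section fixes the reference weight for retention or specifies baseline-weight adjustment for this outcome.

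The R − G result is algebraic. The significance probabilities rest on figures in the plan (5 lb, SD 12 lb, 120 per arm). The precision of change from baseline rests on an assumed correlation, and only the SDs of 12 lb for loss and 15 lb for GWG come from the plan. One secondary outcome is affected. The Table 5 arithmetic and the primary analysis are not.

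**What to change.** In 3.3, 4.7.2 and Table 5:

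- Define postpartum weight retention against a pre-randomisation weight. Compare 12-month weight between arms by linear regression on arm and study-measured baseline weight, and treat 6-week weight in the same way. The arm coefficient is identical to that for change from baseline adjusted for baseline. Pre-pregnancy weight is also fixed before randomisation (4.7.5), but baseline weight is study-measured and starts the primary outcome.
- Keep loss from the 36-week weight as a supportive measure of the postpartum phase. State whether the substitute weights allowed by 5.4.3 count.
- Restate the Table 5 row as a detectable difference at 120 per arm, with its SD labelled as an assumption: about 3.6, 4.4, 5.4 and 7.0 lb at SD 9.9, 12, 15 and 19.2 lb, before any gain from adjustment.

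No new measurements are needed. The stated detectable difference may exceed 4.4 lb, and does so if the assumed SD is above 12 lb (correlation below 0.625). The document is dated May 2016, and 8.1.3 planned for primary-aim data by May 2015. The change should therefore be dated, justified as made without reference to outcome data by arm, and sent for DSMB approval if judged major (7.2.4).
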